8 EFFICACY ANALYSES

The efficacy analysis will be based on all subjects in the SS or FAS, as appropriate. If there is no missing AU flare incidence data from pre-study period, the FAS will be the same as the SS. The FAS will be used for analyses of the primary variable and the SS will be used for all other efficacy analyses. The primary efficacy analysis will additionally be repeated for the PPS.

All statistical analyses besides the primary efficacy analysis will be exploratory in nature only. Any p-values or confidence intervals produced in association with secondary or other analyses will be considered non-confirmatory.

8.1 Statistical analysis of the primary efficacy variable(s)

The primary efficacy analysis will consist of a comparison of the frequency of AU flares during the pre-study/historical period with that observed while in the study during CZP treatment. It is assumed that the frequency of AU flares follows a Poisson distribution. As such, the analysis will be performed as a generalized estimating equations analysis for Poisson outcome that will take into account the possible within-subject correlation (between the retrospective and prospective AU flare counts). The model will contain 2 records per subject corresponding to the frequency of AU flares before study and during the study, offset by log-time of each of the reporting periods. Disease duration of axSpA will be included as a factor in the model, initially defined as <2 years and ≥ 2 years; the specific cutoffs for analysis may deviate from this based on the distribution seen in the data. The p-value for effect of CZP treatment on frequency of AU flares, along with rate ratio (CZP/historical) and 95% confidence interval, will be obtained from this model. The rate per 96 weeks and rate per 2 years for each study period from the model will also be presented.

The primary efficacy analysis hypothesis will be tested based on significance level of alpha 0.05 and will be 2-sided. The analysis of the other secondary efficacy parameters will be supportive. Therefore, no alpha adjustment for secondary efficacy variables will be performed. The alpha adjustment related to the formal interim review of data is described in Section 4.5.

Statistical Model

Let Y_{ij} be the number of AU flare episodes for subject i in period j , where t_{ij} is the length of the interval. It is assumed that the responses within a subject are correlated. For the statistical model assumptions about the correlation structure need to be done. Assuming an exchangeable correlation structure means that correlation between any two responses of the i th individual is the same. Also we account for different interval length by adding the offset term $\log(t_{ij})$. The mean of the Poisson distribution is $E(Y_{ij}) = \mu_{ij}$, and the mean response per unit time is μ_{ij}/t_{ij} . The Poisson model using a log-link can be written as

$$\log \mu_{ij} = \beta_0 + \beta_1 x_{1;ij} + \beta_2 x_{2;i} + \log t_{ij}$$

which resolves to

$$\mu_{ij} = t_{ij} \exp(\beta_0) * \exp(\beta_1 x_{1;ij}) * \exp(\beta_2 x_{2;i})$$

with the variables:

$x_{1;ij}$: variable for period: 1 on-study, 0 pre-study

$x_{2;i}$: variable for disease duration of axSpA: <2 years, ≥ 2 years.

It will be tested whether the period variable has an effect on the response variable. The null hypothesis $H_0: \beta_1=0$ of no difference between periods is tested versus the alternative hypothesis $H_A: \beta_1 \neq 0$ of a difference between periods. This 2-sided test will be based on a significance level of alpha 0.05.

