2.4 Determination of sample size

Based on results from a previous study with CZP in axSpA subjects (AS001), the AU flare rate while treated with CZP is estimated to be 14.6 events per 100 subject-years of exposure. Assuming the rate while treated with CZP represents a reduction in the flare rate of approximately 50%, the AU flare rate for the prestudy period prior to initiation of CZP is estimated to be 29.2 events per 100 subject-years of exposure. A conservative estimate of the sample size for this study is obtained via derivation of the per treatment-group sample size for Poisson regression based on the approach for a 2-group setting initially described by Signorini (1991) and implemented within SAS (Hu, 2008). Assuming an average follow-up period of 1.5 years with 2-sided α -level=0.049 for the final analysis of the primary efficacy variable, a sample size of N=86 subjects per treatment group will have 80% statistical power for a 2 group comparison, corresponding to a total sample size of N=86 subjects for this study with 1 treatment group. Due to the expected increase in statistical efficiency from the fact that each subject serves as his/her own control in the primary efficacy analysis, the actual power for this study is assumed to be >80 percent.

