Unless stated otherwise, all inferential statistical tests will be 2-sided and conducted at the 0.05 alpha level. Adjustment for multiplicity is described in [Section 4.5](#). P-values for secondary efficacy variables are nominal. P-values will be presented to 3 decimal places and any values below 0.001 should be displayed as “<0.001”.

All data in the database (SDTM and ADaM) will be presented in by-subject data listings, and sorted by subject number, parameter (where applicable), and visit (where applicable). For listings including subjects that were not treated, these subjects will be shown first in the listing, ordered by subject number. All listings will include repeated and unscheduled measurements. Such measurements will appear in chronological order together with the scheduled visits, i.e., a repeated measurement will appear directly after the visit and time relative to dosing, for which the repeat measurement was performed. In all the listings dates will be presented in the format ‘YYYY-MM-DD’ and times will be presented in 24h clock format as ‘hh:mm’ or ‘hh:mm:ss’ where appropriate.

All tabulations will be sorted by parameter and visit. Only scheduled visits will be included in the tabulation. Categorical data will be summarized by visit, using the number and percentage of subjects in each category. Percentages will be based on the corresponding population size (i.e., the denominator of percentages should match the sample size in the column header), unless otherwise noted via footnote in the applicable summary table. Percentages will be presented to 1 decimal place. For data points with $n=0$ (i.e., no subjects in the applicable category), no value for percentage of subjects will be displayed.

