4.5 Multiple comparisons/multiplicity

Although there is no intention to stop the study early due to efficacy or futility on the basis of the interim results, $\alpha=0.001$ will be spent in conjunction with this formal interim review of the data (Haybittle, 1971), and the final analysis of the primary efficacy variable will be conducted at the reduced 2-sided α -level of 0.049.

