8.1.1 Derivations of primary efficacy variable

The primary efficacy variable is the number of distinct episodes of AU flares in the Treatment Period. Per protocol, a flare is considered a new episode if a gap of at least 3 months occurs between 2 flares. If AU flare episodes as reported by the investigator occur less than 3 months

(90 days) apart in the same eye, these will be programmatically corrected, such that a new AU flare within 3 months (90 days) after the end of the previous AU flare in the same eye will be considered as pertaining to the same AU episode. These flares will then be counted as one episode. Otherwise, if the time interval between 2 consecutive AU flares is greater than 3 months (90 days), or a separate eye is affected, the AU flares will be considered as separate episodes.

Pre-study and on-study AU flare episodes will be counted. An episode of AU flares is considered as pre-study, if the start date of flare is before the start date of study medication and if start date of flare occurs within the 24 months (730 days) prior to the start of study medication. For the interim analysis, an episode of AU flares is considered as pre-study if the flare occurs within 48 weeks (336 days) prior to the start of study medication.

For the Week 96 (primary) analysis, an episode of AU flares is considered on-study, if the start date of flare is on or after the start date of study medication and the start date of the flare occurs up to and including the last visit in the treatment period, i.e. Week 96 or discontinuation visit.

Pre-study and on-study flares of the same eye will be combined if the time interval between the end of pre-study flare and the start of subsequent on-study flare is less than 3 months (90 days). The resulting flare episode will be considered as pre-study flare episode.

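### Minor inconsistency: SAP 8.1 sets the primary test at two-sided 0.05, which is the overall level; SAP 4.5 and the sample size put the final analysis at 0.049

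*SAP*

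**What the plan says.** SAP 8.1 gives the level twice. Its alpha paragraph says "The primary efficacy analysis hypothesis will be tested based on significance level of alpha 0.05 and will be 2-sided", and that paragraph ends with a pointer: "The alpha adjustment related to the formal interim review of data is described in Section 4.5". After the model equation and the null hypothesis that the period coefficient is zero, the section says "This 2-sided test will be based on a significance level of alpha 0.05", with no pointer and no indication that this is an overall level.

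Three other SAP sections bear on the level:

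- SAP 4.5 spends 0.001 at the interim review and says "the final analysis of the primary efficacy variable will be conducted at the reduced 2-sided" level of 0.049.
- SAP 2.4 uses the same figure: "level=0.049 for the final analysis of the primary efficacy variable, a sample size of N=86".
- SAP 3.9 corrects the protocol's interim level from 0.0001 to 0.001 and presents the final 0.049 as following from the interim spend.

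SAP 3.1 sets the general default and also refers onward: "Unless stated otherwise, all inferential statistical tests will be 2-sided and conducted at the 0.05 alpha level. Adjustment for multiplicity is described in" Section 4.5.

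The protocol has the same split. Section 12.3.1 gives 0.05 for the primary hypothesis. Sections 12.7 and 12.8 use 0.049 for the final analysis.

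A separate wording point concerns the pre-study window. SAP 4.3 still gives 96 weeks for the final analysis, whereas SAP 4.2, 8.1.1 and 8.3.1 give 730 days. SAP 8.1.2 makes the 96-week (672-day) window a sensitivity analysis.

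**The concern.** This is the trial's only confirmatory test; SAP 8 makes everything else exploratory. The threshold for such a test should read the same wherever it is stated. Someone who takes the rule from the model section would use 0.05, and someone who takes it from SAP 4.5 would use 0.049. If the final p-value fell between the two, each reader could cite the SAP, and the question could not be settled credibly once the result was known. The 95% confidence interval planned in SAP 8.1 matches 0.05 rather than 0.049, so in that band it would exclude a rate ratio of 1 while the test at 0.049 failed.

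**Working it through.** **Inputs.** From SAP 2.4: flare rates 0.292 (pre-study) and 0.146 (on CZP) per subject-year, mean follow-up 1.5 years, 80% power, final level 0.049, Signorini two-group Poisson method. From SAP 3.9 and 4.5: interim level 0.001. From SAP 8.1: 0.05. The documents give no correlation between the two looks, so values from 0 to 0.9 are assumed.

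**1. Reproduce N = 86.** Take the pre-study rate as reference and the null variance in the first term, the convention that returns the plan's figure:

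total N = [z(1−α/2)·√4 + z(0.80)·√6]² / [t·λ0·(ln RR)²], with RR = 0.5 and 6 = 2 + 2/RR.

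Denominator: 1.5 × 0.292 × 0.48045 = 0.21044.

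- At 0.049: (2 × 1.9686 + 0.8416 × 2.4495)² = 35.984. Dividing by 0.21044 gives 171.00, or 85.50 per group, rounded up to 86.
- At 0.05: (2 × 1.9600 + 0.8416 × 2.4495)² = 35.778. Dividing gives 170.02, or 85.01 per group, also rounded up to 86.

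The stated N reproduces at 0.049 and would be the same at 0.05.

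**2. How the levels fit together.** 0.001 + 0.049 = 0.050. Read with SAP 4.5, the 0.05 in SAP 8.1 is the total for the two looks and the nominal level of neither.

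**3. Where a conclusion could change.** The critical |z| is 1.960 at 0.05 and 1.969 at 0.049, so only a final p between 0.049 and 0.050 matters.

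- Under the null, the chance is 0.050 − 0.049 = 0.001.
- Under the design assumptions it is the difference in power. With N = 172 in total, power = Φ{[√(N·t·λ0)·|ln RR| − 2z(1−α/2)]/√6}, and √(172 × 0.438) × 0.6931 = 6.016. At 0.05: Φ[(6.016 − 3.920)/2.449] = 0.80395. At 0.049: Φ[(6.016 − 3.937)/2.449] = 0.80200. The difference is 0.00195, about 0.2%.

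**4. Overall type I error.** If no efficacy claim can follow from the interim, the error is that of the final test alone: 0.050 or 0.049.

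If crossing 0.001 at Week 48 did count as a claim, the error is 1 − P(|Z1| < 3.2905, |Z2| < c), with Z1 and Z2 bivariate normal and c the final critical value. At correlation 0 this is 1 − 0.999 × 0.950 = 0.05095 or 1 − 0.999 × 0.951 = 0.04995.

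| Assumed correlation | Final level 0.05 | Final level 0.049 |
|---|---|---|
| 0 | 0.0510 | 0.0500 |
| 0.5 | 0.0506 | 0.0496 |
| 0.707 | 0.0502 | 0.0492 |
| 0.9 | 0.0500 | 0.0490 |

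**The case against.** The strongest reply is that SAP 8.1 already deals with this. It is one section, its alpha paragraph sends the reader to SAP 4.5, and a section need not repeat its own cross-reference a few lines later. SAP 3.1 makes 0.05 a default that yields to more specific text and also names SAP 4.5. SAP 3.9 ties the final 0.049 to the interim spend. On this view 0.05 is plainly the overall level, and nothing has been miscalculated.

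Most of that stands. The level is recoverable, the arithmetic is sound, and the matter is one of wording. What does not stand is that the sentence needs no change. It attaches 0.05 to a specific hypothesis test without calling it overall, and on the sponsor's own scheme no single test is carried out at 0.05.

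A reader might infer that the sentence can refer only to the final test, because SAP 8.1.1 says "For the Week 96 (primary) analysis, an episode of AU flares is considered on-study", and so that it contradicts SAP 4.5 outright. The documents do not support that. The label introduces a counting window. SAP 4.3 has the interim follow the final specifications unless stated otherwise, and SAP 8.1.1 gives interim windows and offsets for the same model. The model and its null hypothesis serve both looks.

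A reader might also infer that the type I error is inflated. That would require a final test at 0.05 and an interim crossing that counted as a claim. SAP 4.5 says "Although there is no intention to stop the study early due to efficacy or futility on the basis of the interim results" and does not say that any claim would be made at Week 48.

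**Conclusion.** There is a minor internal inconsistency. SAP 8.1 prints the overall level where a reader needs the nominal one; the final analysis is meant to be tested at two-sided 0.049, and the SAP allows that to be worked out. The practical reach is a final p between 0.049 and 0.050.

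The figure of about 0.2% rests on the two-group design assumptions. The plan expects power above 80% because subjects serve as their own controls, which would make it smaller. The ceiling of 0.0510 on overall error rests on two things the documents do not state: that an interim crossing would be a claim, and that the looks are uncorrelated. With a final level of 0.049, overall error stays at or below 0.05 at every correlation tried. Sample size is not affected.

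The 96-week wording in SAP 4.3 is a separate tidying item with no bearing on alpha.

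**What to change.** - **SAP 8.1**, in both the alpha paragraph and the sentence after the null hypothesis: state two-sided 0.05 overall, with 0.001 at the Week 48 interim and 0.049 at the final Week 96 analysis (Section 4.5).
- **SAP 3.9**: add that the 0.05 in Protocol 12.3.1 is the overall level, with 0.049 at the final analysis as in Protocol 12.7.
- **SAP 4.3** (separate item): replace the 96-week pre-study wording for the final analysis with a reference to SAP 8.1.1.

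The cost is one sentence in each place. The fix adopts the sponsor's own levels and needs no protocol amendment and no change to N or data collection.

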8.1.1 Derivations of primary efficacy variable

The primary efficacy variable is the number of distinct episodes of AU flares in the Treatment Period. Per protocol, a flare is considered a new episode if a gap of at least 3 months occurs between 2 flares. If AU flare episodes as reported by the investigator occur less than 3 months

(90 days) apart in the same eye, these will be programmatically corrected, such that a new AU flare within 3 months (90 days) after the end of the previous AU flare in the same eye will be considered as pertaining to the same AU episode. These flares will then be counted as one episode. Otherwise, if the time interval between 2 consecutive AU flares is greater than 3 months (90 days), or a separate eye is affected, the AU flares will be considered as separate episodes.

Pre-study and on-study AU flare episodes will be counted. An episode of AU flares is considered as pre-study, if the start date of flare is before the start date of study medication and if start date of flare occurs within the 24 months (730 days) prior to the start of study medication. For the interim analysis, an episode of AU flares is considered as pre-study if the flare occurs within 48 weeks (336 days) prior to the start of study medication.

For the Week 96 (primary) analysis, an episode of AU flares is considered on-study, if the start date of flare is on or after the start date of study medication and the start date of the flare occurs up to and including the last visit in the treatment period, i.e. Week 96 or discontinuation visit.

Pre-study and on-study flares of the same eye will be combined if the time interval between the end of pre-study flare and the start of subsequent on-study flare is less than 3 months (90 days). The resulting flare episode will be considered as pre-study flare episode.

The log-time offset in the Poisson model will consist of the length of pre-study and on-study reporting periods in days. As the documentation of pre-study episodes is extended to up to 2 years prior to Baseline, the pre-study period length for offset is 730 days for each subject, unless the date of first uveitis flare is within 2 years of baseline, in which case the pre-study period length will be from date of first uveitis flare until baseline. The on-study period length for offset is the time in days from start of study medication until last visit, i.e. Week 96 or discontinuation visit. For the interim analysis, an offset of 336 days will be used for the pre-study period or time since first uveitis flare if shorter than 336 days, and the time in days from start of study medication until week 48 visit (taken as 336 days) or early termination visit (taken as 14 days after the last treatment) where applicable will be used for the on-study period.

Disease duration of axSpA, which will be included in the Poisson model as a factor, is calculated as defined in Section 6.2, and is categorized into <2 years and ≥ 2 years.

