8.1.2 Supportive and sensitivity analyses of the primary efficacy variable

The primary efficacy analysis will be repeated in the subgroup of subjects with at least 1 documented AU flare within 12 months prior to Baseline.

The AU flares as reported by the investigators, without programmatically correcting for the 3 month interval between 2 flares, will be analyzed in addition to the primary efficacy variable of protocol-defined AU flares at least 3 months apart.

The primary analysis will be repeated using the pre-study period as 96 weeks (672 days) prior to start of study medication for counting flares and as the offset, instead of 24 months. The on-study period will be the same as that used for the primary analysis.

In addition, the analysis for the full 2 years before and after study medication will be provided. The pre-study period will be the 2 years (730 days) prior to start of study medication, which will be used for counting flares and as the offset. The on-study period will be determined for whose episodes of AU flares for which the start date of flare is on or after the start date of study

medication and up to and including the SFU visit or date of last administration of study medication + 70 days.

An analysis for the first 48 weeks will also be produced. The period for pre-study will be the 12 months (365 days) prior to start of study medication, which will be used for counting flares and as the offset. An episode of AU flares will be considered on-study, if the start date of flare is on or after the start date of study medication and up to and including the Week 48 visit or discontinuation visit if prior to Week 48. The exact date of the Week 48 or discontinuation visit will be used for each subject. This analysis will also be repeated using 48 weeks (336 days) as the pre-study period for counting flares and as offset, but keeping the on-study period of 48 weeks the same (i.e. using the exact date of the Week 48 or discontinuation visit).

The primary efficacy analysis will be repeated in the subgroup of subjects excluding those with any pre-study flares with completely missing end dates in the 2 years prior to baseline. Subjects will be excluded if any of the flares that started within the 2 years prior to baseline have completely missing end dates (i.e. no day, month or year)

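### The first-ever uveitis flare both starts the pre-study clock and counts as an event, which inflates the historical rate and biases the primary rate ratio towards certolizumab pegol

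*SAP*

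**What the plan says.** The primary analysis (SAP 8.1) is a Poisson GEE with two records per subject, pre-study and on-study, each offset by the log of its period length. SAP 8.1.1 defines the inputs:

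- **Pre-study count.** An episode counts if it starts before first dose and "if start date of flare occurs within the 24 months (730 days) prior to the start of study medication". The first-ever flare is not excepted.
- **Pre-study time.** By default, "the pre-study period length for offset is 730 days for each subject". If the first uveitis flare was within 2 years of Baseline, the exception applies: "in which case the pre-study period length will be from date of first uveitis flare until baseline".
- **On-study time.** "The on-study period length for offset is the time in days from start of study medication until last visit".
- **Interim analysis.** The offset is 336 days, "or time since first uveitis flare if shorter than 336 days".

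SAP 8.1.2 adds supportive repeats with fixed pre-study windows of 672 and 730 days. For the latter, "The pre-study period will be the 2 years (730 days) prior to start of study medication". Both count the first flare.

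**The concern.** If time before the first-ever flare is treated as not at risk, the flare that opens the risk period cannot also be an outcome in it. Under the SAP rule each affected subject brings one guaranteed episode at time zero and a shortened denominator. A single flare 60 days before Baseline is recorded as 1 episode in 60 days, about 6 per year (365/60). First dose is not a flare, so the on-study record has no matching guaranteed event.

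The only covariate is axSpA disease duration. It is measured from axSpA onset (SAP 6.2) and enters as a main effect without a period interaction, so it does not correct the imbalance.

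The trial has one arm. The historical rate is the sole comparator and this is the only confirmatory test. A rule that raises the historical rate therefore lowers the rate ratio (CZP/historical) and can produce a significant result with no drug effect.

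**Working it through.** **Inputs.** SAP 2.4 gives a rate on treatment that "is estimated to be 14.6 events per 100 subject-years of exposure", a pre-study rate "estimated to be 29.2 events per 100 subject-years of exposure", 1.5 years' average follow-up, alpha 0.049 and N=86. The share *f* of subjects with a first flare within 2 years of Baseline is not given, so it is ranged. Assumption: the time *T* from first flare to Baseline is uniform on 0 to 2 years (mean 1 year).

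**The plan's own figure.** The cited Signorini form gives

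[z(0.9755)·√4 + z(0.80)·√(2 + 2/0.5)]² / (1.5 × 0.292 × (ln 0.5)²) = 171.0 in total,

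or 85.5 per group, rounded up to 86. This reproduces N=86, which is not in dispute.

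**Expected null rate ratio.** Let λ be the true yearly rate in both periods. An affected subject contributes 1 + λT expected episodes over T years, a rate of λ + 1/T. Any other subject contributes 2λ over 2 years. Pooling:

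- pre-study rate = [(1−f)·2λ + f·(1+λ)] / [(1−f)·2 + f·1]
- null RR = λ / pre-study rate

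For λ = 0.292 and f = 20%: (0.8 × 0.584 + 0.2 × 1.292) / 1.8 = 0.7256 / 1.8 = 0.403 per year, and RR = 0.292 / 0.403 = 0.72. With a fixed 730-day offset and the flare still counted: 0.7256 / 2 = 0.363 and RR = 0.80. With the truncated clock and that flare not counted, numerator and denominator are proportional and RR = 1.00 for every f.

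| f | Pre-study rate per 100 PY, SAP rule | RR, SAP rule | RR, fixed 730 days | RR, first flare not counted |
|---|---|---|---|---|
| 0% | 29.2 | 1.00 | 1.00 | 1.00 |
| 5% | 31.8 | 0.92 | 0.94 | 1.00 |
| 10% | 34.5 | 0.85 | 0.89 | 1.00 |
| 20% | 40.3 | 0.72 | 0.80 | 1.00 |
| 30% | 46.8 | 0.62 | 0.73 | 1.00 |

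**Dependence on the true rate** (SAP rule, null RR):

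| True rate per 100 PY | f = 10% | f = 20% | f = 30% |
|---|---|---|---|
| 14.6 | 0.74 | 0.57 | 0.45 |
| 29.2 | 0.85 | 0.72 | 0.62 |
| 50 | 0.90 | 0.82 | 0.74 |
| 100 | 0.95 | 0.90 | 0.85 |

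**False-positive rate at 29.2 per 100 PY, n=86, alpha 0.049.** Two simulations were run: (A) a robust Wald test with 1.5 years on study, 10,000 trials per scenario; (B) the Poisson GEE with exchangeable correlation and 672 days on study, 400 trials per scenario, without the disease-duration factor. Two-sided rejection:

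| f | SAP rule, A | SAP rule, B | Fixed 730 days, A | First flare not counted, B |
|---|---|---|---|---|
| 0% | – | 6.0% | – | 6.0% |
| 5% | – | 5.5% | – | 4.0% |
| 10% | 12% | 14.0% | 8% | 4.3% |
| 20% | 35% | 37.2% | 19% | 5.5% |
| 30% | 66% | 74.5% | 36% | 7.2% |

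With the first flare not counted, A gives about 5%. B has more on-study time, hence more power against a shifted ratio, and carries Monte Carlo error of about 1 to 2.5 points. Under the SAP rule, nearly all rejections from f = 10% upwards favour CZP.

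**Estimate when the drug works.** If the planned halving were true and f = 20%, the reported ratio would be about 0.146 / 0.403 = 0.36 instead of 0.50.

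**The case against.** The mechanism is hard to dispute, but its size rests on two unknowns.

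- **The share affected.** *f* appears nowhere in the documents, and inclusion criterion 7 (Protocol 6.1) could not be read in full in the text used here. If *f* is zero there is no bias. At 5% the GEE simulation shows no visible inflation of the error rate, although the ratio is already 0.92. This stands.
- **The rate.** 29.2 is not a measurement. It is the on-treatment estimate doubled under an assumed 50% reduction. At 100 per 100 PY the ratio at f = 20% is 0.90, not 0.72. This stands, but it works both ways: at 14.6 the ratio is 0.57.
- **Truncation is the smaller part at the planning rate.** At f = 20%, counting the first flare over a fixed 730 days gives 0.80; truncating the clock adds only 0.08. The 60-day example also overstates one subject's leverage, because the model is close to a pooled rate. Both are correct, and they point to the counted flare as the item to correct.
- **The SAP already shows the problem.** It tabulates time since first flare (<2 and ≥2 years) and plans fixed-window repeats. These are supportive only and still count the first flare. The subgroup with a flare in the last 12 months keeps every subject whose first flare fell in that year, so the artefact would be concentrated there.
- **The 90-day same-eye merging rule was not simulated above.** After an excluded first flare, no new same-eye episode can count for a while. Assuming 42-day flares, the corrected ratio was 1.00 to 1.05, slightly against CZP. This is small beside the bias removed, but the wording should deal with it.

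Between-subject heterogeneity does not help: with gamma variance 1 and f = 20%, the ratio stayed at 0.72 with 34% to 37% rejection.

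**Conclusion.** The concern holds. For any subject with a first-ever flare inside 2 years, the primary rule gives an expected pre-study rate above the true one, and nothing in the model offsets it. The direction is certain for any *f* above zero.

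The size is conditional. At 29.2 per 100 PY and uniform first-flare timing, null rate ratios are 0.85, 0.72 and 0.62 at 10%, 20% and 30% affected, with false-positive rates of about 12%, 35% and 66%. At 5% the effect on the error rate is negligible. Higher true rates shrink the bias and lower ones enlarge it; none reverses it. Because the rule sits in the only confirmatory test, it should be corrected whatever *f* turns out to be.

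**What to change.** In SAP 8.1.1, state that when the pre-study window is truncated at the first-ever flare, that episode is not counted: only later episodes count, over the time after it. Apply the same rule to the 336-day interim window and to the 8.1.2 repeats that reuse the primary method. Report how many subjects are affected.

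Add a line on merging. SAP 8.1.1 assigns an on-study flare within 90 days of a pre-study flare in the same eye to the pre-study episode. If that episode is the excluded one, the on-study flare would be counted nowhere. Simulation suggests 0.04 to 0.28 such flares per trial. The SAP should say where they go, with a sensitivity analysis counting them as on-study.

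A fixed pre-study offset is a weaker fallback: it reduces the bias at the planning rate without removing it. The 672-day repeat is the cleaner comparator because it keeps the primary on-study window. The 730-day repeat also extends on-study time to the safety follow-up visit or last dose + 70 days.

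The cost is a sentence or two of SAP text and minor programming, with no new data. The historical rate, and so the apparent effect, becomes less favourable. Subjects whose only pre-study flare was their first contribute time but no event. The planned information is kept: at f = 20%, pre-study time is 86 × 1.8 = 154.8 subject-years, or 154.8 × 0.292 = 45.2 expected episodes, against 86 × 1.5 × 0.292 = 37.7 in the sample-size calculation.
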